## List of Abbreviations

|      |                                    |
|------|------------------------------------|
| ST   | SmartTouch                         |
| STSF | SmartTouch SF                      |
| AF   | Atrial Fibrillation                |
| VT   | Ventricular Tachycardia            |
| EHR  | Electronic Health Records          |
| AAD  | Antiarrhythmic Drugs               |
| BMI  | Body Mass Index                    |
| CABG | Coronary Artery Bypass Grafting    |
| MI   | Myocardial Infarction              |
| PCI  | Percutaneous Coronary Intervention |

## 1. Study Rationale and Design

This study aims to provide evidence using real-world data supporting a label expansion of ThermoCool catheters for patients with persistent atrial fibrillation (AF) or ischemic ventricular tachycardia (VT). Retrospective real-world data from Mercy and Mayo Clinic electronic databases will be used. The first indication expansion being sought is for the ThermoCool Smarttouch® (ST) catheter to treat persistent AF. An investigational device exemption clinical study was conducted for a label expansion for the ThermoCool Smarttouch® SF (STSF) catheter for persistent AF [1] and approved on September 30, 2020 under PMA supplement P030031/S100. This study will use ThermoCool STSF as the comparator to expand the labelled indication for ThermoCool ST among persistent AF patients. The second indication expansion is for the ThermoCool STSF catheter to include an indication for the treatment of ischemic VT (defined by the presence of a history of myocardial infarction (MI) prior to the index ablation procedure in this study). The ThermoCool ST catheter has a label for ischemic VT. Among patients who had procedures performed with ThermoCool STSF, this study will compare the safety outcomes to a performance goal in order to expand the labelled indication among ischemic VT patients.

### 1.1 Primary Objectives

The primary objectives are:

- 1) To evaluate the non-inferiority of ablation with the ThermoCool ST catheter relative to the ThermoCool STSF catheter for the treatment of persistent AF on a composite safety endpoint.
- 2) To evaluate ablation with the ThermoCool STSF catheter relative to a performance goal for the treatment of ischemic VT on a composite safety endpoint.

Determinations about non-inferiority with respect to safety for the first objective (persistent AF) will be based on a hypothesis test of the subject device relative to the comparator device with respect to absolute risk (i.e., risk difference) using data balanced on pre-specified measured covariates. Hypothesis testing for the second objective (ischemic VT) will compare the cumulative incidence of a composite safety endpoint in the subject device group to a performance goal using unadjusted data.

### 1.2 Exploratory Objectives

The exploratory objectives are:

- To describe the effectiveness of ablation with the ThermoCool ST catheter relative to ThermoCool STSF for the treatment of persistent AF using the propensity score balanced data.

- To describe the effectiveness of ablation with the ThermoCool STSF catheter for the treatment of ischemic VT using the unadjusted data.
- To describe the safety of ablation with the ThermoCool STSF catheter for the treatment of overall VT on a composite safety endpoint using the unadjusted data. The overall VT population will be identified using the same criteria as ischemic VT except removing the requirement of prior MI.
- To describe the safety of ablation with the ThermoCool STSF catheter in a subgroup that excludes non-ischemic cardiomyopathy patients using a composite safety endpoint in the ischemic VT population using the unadjusted data.
- Explore the sensitivity of the safety results for persistent AF to hospital bed size. Remove hospital bed size as a balancing variable for patients with persistent AF in the Mayo data source. Perform the balanced outcome analysis with this modification in Mayo and recalculate an average difference (all Mercy hospital bed sizes were above the prespecified bed size cut point of 500 so this covariate was not included in the Mercy propensity score model).
- Explore the sensitivity of the safety results for ischemic VT by performing an outcome analysis comparing the ThermoCool STSF group to the ST group using the balanced data.
- Perform exploratory subgroup analyses among patients with a prior prescription of class I or III AAD before the index ablation procedure for the persistent AF population using propensity score balanced data.

Determinations about comparative effectiveness and safety of these exploratory objectives will not be based on hypothesis tests, rather examination of point and confidence interval estimates within each group and differences.

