#### 4.6.2 Method for Covariate Balancing

We considered several PS methods to maximize balance [7] (see appendix, tables 1-4). For ischemic VT, none of the methods considered adequately balanced the data, therefore a comparative design was not pursued in favor of single arm design using a performance goal [8]. For persistent AF a singular method that minimizes imbalance across the two data sources was selected, average treatment effect on the treated weights [9] with weight trimming/winsorizing [10]. Specifically, patients receiving the subject device receive a weight of 1 and those receiving the comparator device (c) receive a weight based on the odds,  $w_i = \frac{\hat{e}_i}{1-\hat{e}_i}$ , where  $\hat{e}_i$  = estimated propensity score for patient  $i = 1, \dots, n_c$ . Furthermore, patient weights in the comparator group only are trimmed/winsorized at the 95th percentile of the weight distribution (i.e., all weights with value above the 95th percentile are set equal to the 95th percentile).

When used with logistic regression to estimate the propensity score, weight trimming has been shown to reduce bias in estimating the treatment effect when the model is mis-specified due to non-linear and non-additive effects, as well as to increase precision of the estimated treatment effects [10]. Use of untrimmed ATT weights has been shown unbiased in simulation studies in estimating the risk difference using survival data [11].

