#### 4.7 Outcome Analysis

For persistent AF, the primary objective is to estimate the covariate balanced risk difference comparing the subject device and the comparator device within each data source and

subsequently averaged across data sources, with the average used for hypothesis testing of non-inferiority for the safety endpoint. Additionally, descriptive analyses for the safety endpoint will be conducted (e.g., unbalanced outcome analysis), as well as exploratory analyses (1.2).

For ischemic VT, the primary objective is to estimate the proportion of patients with safety events who received ThermoCool STSF (unbalanced data), pooled across the two data sources and used to compare against a performance goal for hypothesis testing purposes, following the recommendations of Lu et al [8], since covariate balance was not achieved through propensity score balancing approaches. Descriptive analyses for the safety endpoint will be conducted (e.g., proportion with safety events within catheter group and within data source). Descriptive analyses for the safety endpoint will be conducted in patients who received ThermoCool ST for contextualizing the ThermoCool STSF results. Additional exploratory analyses will also be conducted (1.2).

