## 6. Summary of Revisions to the Original Version of the SAP

Five candidate designs based on the propensity score were evaluated by the independent statistician who had access to data on the catheter group at the index procedure (STSF or ST) and the covariates for each of the four study populations (AF Mayo, AF Mercy, VT with prior MI Mayo, VT with prior MI Mercy), *but no access to the outcome data*. Based on covariate balancing results the following major changes were adopted to the SAP:

- 1) For the persistent AF patient populations in both Mayo and Mercy, average treatment effect on the treated (ATT) weights will be used, with weights above the 95th percentile of the weight distribution trimmed/winsorized (i.e., set equal to the 95th percentile).
- 2) Bootstrapping was originally proposed as a method to calculate the variance of the survival estimate within each catheter group for the covariate balanced persistent AF data. However, bootstrapping performed by the independent statistician resulted in extremely large weights even after trimming (e.g., due to positivity violations in the bootstrap samples). For this reason, the infinitesimal jackknife [17,18] will be used instead for variance calculations in the comparator arm.
- 3) In consideration of inadequate covariate balance achieved for the ischemic VT data, as well as the possibility of zero events in one or more catheter groups in the two data sources, a comparative analysis was not pursued in favor of single arm design using a performance goal, as proposed by Lu et al. [8]. Instead, the primary objective for the ischemic VT patient populations is to evaluate whether patients with ischemic VT, who had a procedure performed with ThermoCool STSF (pooled across Mercy and Mayo), result in safer outcomes than a performance goal for the composite safety endpoint.

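### The exploratory ischemic VT comparison of STSF with ST is to run on balanced data, yet the SAP reports that VT balance was not achieved and fixes no VT weighting method

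*SAP*

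**What the plan says.** Section 1.2 lists this among the exploratory objectives: "Explore the sensitivity of the safety results for ischemic VT by performing an outcome analysis comparing the ThermoCool STSF group to the ST group". The sentence ends by naming the data to be used: "comparing the ThermoCool STSF group to the ST group using the balanced data". It is framed as a sensitivity check on the VT safety result. The other ischemic VT objectives in that list specify unadjusted data. The section closes with this limit: "Determinations about comparative effectiveness and safety of these exploratory objectives will not be based on hypothesis tests".

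Three other places describe what balancing achieved for VT:

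- Section 4.6.2: "For ischemic VT, none of the methods considered adequately balanced the data, therefore a comparative design was not pursued".
- Section 4.7, explaining the single-arm design: "since covariate balance was not achieved through propensity score balancing approaches".
- Section 6, item 3: "In consideration of inadequate covariate balance achieved for the ischemic VT data", together with possible zero events in some groups, "a comparative analysis was not pursued in favor of single arm design using a performance goal".

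Section 4.6 limits the balancing method to persistent AF. Section 4.6.2 selects ATT weights winsorized at the 95th percentile for persistent AF. Sections 4.7.1 to 4.7.3 give the risk difference, its variance and the pooling rule under persistent AF headings. Section 4.7.4 gives VT a simple proportion with Clopper-Pearson limits. The Table 6 shell has STSF and ST rows by source but no row for their difference. Appendix Tables 3 and 4 show ASDs for the candidate VT designs without choosing one.

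**The concern.** The objective refers to a data set that the rest of the SAP says could not be produced to an adequate standard. Two problems follow.

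First, the analysis cannot be run from the SAP as written. Nothing says which candidate weights apply to VT, or which estimator, variance and pooling rule go with them. Section 4.5 separates design from outcome so that such choices are made blind. A choice left open until the balanced data are linked back to outcomes weakens that protection for this analysis.

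Second, the label matters for interpretation. A result reported as a balanced comparison, and used to support a primary safety finding, would be read as adjusted for the listed covariates. The Appendix shows that under every candidate design it would be adjusted only in part.

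**Working it through.** **Inputs.** ASDs, their counts above 0.20 and their means come from Appendix Tables 3 (Mercy) and 4 (Mayo). Group sizes come from Table 1: 35 STSF and 23 ST in Mercy, 35 STSF and 84 ST in Mayo. The assumed risk of 7.5% comes from Section 3 for STSF. Section 4.8 implies the same figure for ST, since the goal of 0.15 is twice the anticipated ST risk.

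**Reproducing the plan's figures.** Counting and averaging the 16 rows of Table 3 returns the printed summaries exactly: 9, 9, 14, 14, 10, 9 above 0.20, and means 0.37, 0.60, 0.45, 0.45, 0.33, 0.31. The crude ASDs also follow from the printed counts by the Section 4.6.3 formula, |p_s − p_c| / √{[p_s(1 − p_s) + p_c(1 − p_c)]/2}:

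- Mercy ICD/pacemaker, 33/35 against 12/23: 0.4211 / √0.1517 = 1.081, as printed.
- Mayo index year 2014-18, 5/35 against 68/84: 0.6667 / √0.1383 = 1.793, as printed.

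For Mayo, the 18 rows available to me give 7, 17, 17, 16, 3, 3 above 0.20, against the printed 8, 17, 18, 17, 4, 4. Five of the six counts are one lower, which would fit one covariate row not being shown. I use the printed totals; the conclusion is the same either way.

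**Residual imbalance under each candidate.**

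| | Crude | Strata | Untrimmed | Trim 99 | Trim 95 | Trim 90 |
|---|---|---|---|---|---|---|
| Mercy: ASDs > 0.20 | 9 | 9 (4 rows NA) | 14 | 14 | 10 | 9 |
| Mercy: mean ASD | 0.37 | 0.60 | 0.45 | 0.45 | 0.33 | 0.31 |
| Mercy: ICD/pacemaker | 1.081 | 0.908 | 1.108 | 1.108 | 0.972 | 0.915 |
| Mayo: ASDs > 0.20 | 8 | 17 | 18 | 17 | 4 | 4 |
| Mayo: mean ASD | 0.27 | 0.98 | 0.72 | 0.49 | 0.16 | 0.17 |
| Mayo: index year | 1.793 | 0.458 | 0.462 | 0.332 | 1.019 | 1.066 |

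**Carrying over the AF rule (95% trimming).**

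- In Mercy the ten rows above 0.20 are age 0.778, sex 0.649, race 0.296, index year 0.343, BMI 0.262, stroke 0.225, hypertension 0.548, diabetes 0.299, valve replacement 0.301 and ICD/pacemaker 0.972. Eight of the 16 are larger than before weighting: age (from 0.581), sex (0.372), race (0.080), BMI (0.150), stroke (0.188), hypertension (0.383), diabetes (0.134) and valve replacement (0.080).
- In Mayo the count falls from 8 to 4 and the mean from 0.27 to 0.16, but index year stays at 1.019 and ICD/pacemaker at 0.421.

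**The wording does not identify a column.** By mean ASD the least imbalanced candidate is 90% trimming in Mercy (0.31) and 95% trimming in Mayo (0.16).

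**Zero-event arms.** At a risk of 7.5%, the chance of no events is 0.925^23 = 0.166 in Mercy ST, 0.925^35 = 0.065 in each STSF arm and 0.925^84 = 0.001 in Mayo ST. The chance that at least one of the four arms has none is 1 − (0.834)(0.935)²(0.999) = 0.27, taking the arms as independent. Any VT comparison method therefore has to cope with an empty arm.

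**The case against.** The other side has a good deal on its side.

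- **No decision depends on it.** Section 1.2 excludes hypothesis tests for exploratory objectives. Section 5 bases VT success in Mercy/Mayo on the STSF group alone: either the test against the performance goal, or the STSF point estimate alongside the separate Premier study. This stands and limits the point's weight.
- **The label may be loose wording.** A reader might infer that a heavily confounded contrast would be passed off as balanced. The SAP does not support that. It states the VT balance failure three times and prints the ASDs for every candidate. It also uses the same label for Mayo AF, where hospital bed size stays at 1.599 after 95% trimming. Confounding here is inferred from measured imbalance; no bias has been estimated.
- **Weighted VT designs do exist.** A reader might infer that there is no VT data set to analyse. Candidate designs were built in both sources, and their covariates can be read from Tables 3 and 4. The gap is narrower: none is selected, and none is adequate by the SAP's own judgement.
- **Mayo is not the clear failure.** At 95% trimming, Mayo VT (4 above 0.20, mean 0.16) is on those summaries no worse than the Mayo AF design the SAP accepts (6, mean 0.18), although VT index year remains near 1.0.
- **Zero events.** A reader might infer that the plan applies Wald limits and inverse-variance pooling to sparse VT arms. It assigns those methods to persistent AF only. For VT the fault is that no comparison method is stated.

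What remains is that Section 1.2 conflicts with Sections 4.6.2, 4.7 and 6, and that the objective cannot be carried out as specified.

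**Conclusion.** The inconsistency is real and goes beyond missing detail: whichever candidate were used, this sensitivity check would rest on data the SAP itself says were not adequately balanced. The shortfall is plainest in Mercy, where the AF rule leaves 10 of 16 ASDs above 0.20 against 9 crude and makes half the covariates worse. In Mayo the same rule improves the summaries but leaves index year at 1.019. Those figures assume that the AF rule would be the one carried over, which the SAP does not say.

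The consequence is confined to the reading of one exploratory result. The primary VT test, the success rule and the persistent AF analysis are unaffected. It should be corrected because it is presented as support for a primary safety finding and the correction is easy.

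**What to change.** Either of two changes would do.

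1. Delete the reference to balanced data in that Section 1.2 objective. Report the STSF and ST proportions by source, which Section 4.7 and the Table 6 shell already plan, and add an unadjusted difference with an exact or score interval. Label it descriptive and confounded, because without weighting the Mayo index-year ASD is 1.793 and the Mercy ICD/pacemaker ASD is 1.081.
2. If a weighted contrast is kept, state the VT weights, covariates, estimator, variance and pooling rule before outcomes are linked, using methods that can handle an arm with no events. Call the result incompletely adjusted and print the residual ASDs beside it.

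The first costs a wording change and a difference row in Table 6. The second needs a short added methods section. Neither needs new data or touches a primary analysis.

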## 2. Analysis Data Sets

The primary objective will be evaluated on two separate patient populations. The inclusion/exclusion criteria for the **persistent AF population** consists of including patients meeting all the following:

- Underwent an intracardiac catheter ablation for AF by pulmonary vein isolation
- Had a primary or secondary diagnosis of persistent AF associated with the same intracardiac catheter ablation procedure encounter
- The index procedure for a patient is the first recorded intracardiac catheter ablation for AF by pulmonary vein isolation with a primary or secondary diagnosis of persistent AF
- Index procedure performed using the ThermoCool ST catheter or ThermoCool STSF catheter
- At least 18 years of age or older at the time of the index procedure
- At least 6 months of encounter history prior to the index procedure

And excluding patients meeting any of the following:

- Received both the device of interest (ThermoCool ST catheter) and the comparator device (ThermoCool STSF catheter)
- Underwent an intracardiac catheter ablation prior to the index procedure
- Had a surgical cardiac ablation any time prior to or at the same time as the index procedure
- Had a concomitant left atrial appendage occlusion procedure at the time of the index procedure
- Had a concomitant atrioventricular node ablation at the time of the index procedure
- Had a prior heart transplant or long-term heart assist system implantation prior to the index procedure

The inclusion/exclusion criteria for **ischemic VT** consist of including patients meeting all the following:

- Underwent an intracardiac catheter ablation for VT
- Had a primary or secondary diagnosis of VT associated with the same intracardiac catheter ablation procedure
- The index procedure for a patient is the first recorded intracardiac catheter ablation for VT with a primary or secondary diagnosis of VT
- Index procedure performed using the ThermoCool STSF or ThermoCool ST catheter
- At least 18 years of age or older at the time of the index procedure
- At least 6 months of encounter history prior to the index procedure
- Any myocardial infarction diagnosis prior to the index procedure

And excluding patients meeting any of the following:

- Received both the device of interest (ThermoCool STSF) and the comparator device (ThermoCool ST)
- Underwent an intracardiac catheter ablation prior to the index procedure
- Had a surgical cardiac ablation prior to or at the time of the index procedure
- Had a prior heart transplant or long-term heart assist system implantation prior to the index procedure
- Patients with less than 7 days of follow-up due to administrative censoring\*

\* This censoring event will be present if the latest date of follow-up - date of index procedure < 7 days. The latest date of follow-up is determined by the date that the data is extracted from the EHR.

### 3. Sample Size Justification

Sample size calculations are based on statistical power for the primary objectives (i.e., safety analyses) proposed in this study. The minimum required sample size was calculated separately for the planned hypothesis tests of non-inferiority of the composite safety endpoint in the persistent AF cohort and ischemic VT cohorts. Below are the details of power calculations.

For persistent AF, hypothesis tests are based on two-group comparison data pooled across data sources using the upper bound of the two-sided 90% Wald confidence interval (section 4.7.3). For this reason, power calculations use a two-sample test for a difference in proportions based on a Pearson chi-square test as implemented in PROC POWER in SAS, version 9.4. For persistent AF, we assume the composite safety endpoint proportion is 0.07 in both arms (i.e., an assumed population difference in proportions of 0), a non-inferiority margin of 0.07, and a one-sided test at the 0.05 alpha-level to determine the minimal N which provided more than 80% power; this sample size was 330 (or 165 per group).

For ischemic VT, hypothesis testing is based on a single group (ThermoCool STSF) with data pooled across the two data sources using the upper bound of the two-sided 90% confidence interval for a one-sample exact test of a proportion (section 4.7.4). For this reason, power calculations use a one-sample exact test for a proportion as implemented in PROC POWER in SAS, version 9.4. For ischemic VT, we assume the composite safety endpoint proportion is 0.075, a performance goal of 0.15, and a one-sided test at the 0.05 alpha-level. Given the sample size of 70 (Table 1), the estimated power is 57%.

Based on the sample sizes available (Table 1), the study is likely adequately powered for persistent AF, but less than adequately powered for ischemic VT.

Table 1. Available Sample Sizes for Each Study Population After Inclusion/Exclusion Criteria Are Applied

|                                    | ST (test)   | STSF (comparator) |
|------------------------------------|--------------------|--------------------------|
| Persistent AF               |                    |                          |
| Mercy                              | 186                | 763                      |
| Mayo Clinic                        | 337                | 164                      |
| Total                       | 523                | 927                      |
|                                    | STSF (test) | ST (reference)    |
| Ischemic VT (with prior MI) |                    |                          |
| Mercy                              | 35                 | 23                       |
| Mayo Clinic                        | 35                 | 84                       |
| Total                       | 70                 | 107                      |

